Official Study Title:

The Clinical Effects of Kinesio Taping Versus Sham Taping on Pain, Kinesiophobia, Functional Mobility, and Disease Activity in Patients with Rheumatoid Arthritis: A Randomized Controlled Trial

ClinicalTrials.gov Identifier (NCT Number):

NCT0XXXXXXX

Document Date:

30 October 2024

Principal Investigator:

[name]

Istanbul Rumeli University, Faculty of Health Sciences, Department of Physiotherapy and Rehabilitation

The Effectiveness of Kinesiology Taping in Patients with Knee Rheumatoid Arthritis in Terms of Pain, Function and Kinesiophobia: A Randomised Controlled Trial

Background:**Background:**

Rheumatoid arthritis is a chronic inflammatory disease that leads to joint pain, reduced

functional capacity, and movement-related fear. Non-pharmacological and supportive treatment methods are increasingly emphasized to improve patients' quality of life. Kinesio taping has been suggested as a potential complementary approach, but its clinical benefits compared to sham applications remain uncertain.

Objective:

The aim of this study is to investigate the effects of kinesio taping compared to sham taping in patients with rheumatoid arthritis, with a particular focus on pain, functional mobility, kinesiophobia, and disease activity.

Methods:

A randomized controlled design is planned, including 30 patients with rheumatoid arthritis aged 45–65 years with moderate disease activity (DAS28: 2.6–5.1). Participants will be randomly assigned to two groups: kinesio taping or sham taping. Interventions will be applied twice a week for four weeks. Outcomes will include pain (Visual Analog Scale), disease activity (DAS28), kinesiophobia (Tampa Kinesiophobia Scale), and functional mobility (Timed Up-and-Go Test). Measurements will be taken before and after the intervention period.

Ethical Approach: All procedures conform to the ethical standards of the Helsinki Declaration and were approved by the Istanbul Rumeli University Ethics Committee.

The Statistical analysis: The statistical evaluation of the study data will be carried out using IBM SPSS Statistics version 26.0. The distribution of quantitative variables will be examined with the Kolmogorov-Smirnov test to determine normality. Between-group comparisons of categorical variables will be performed with the Chi-square test, while continuous variables will be analyzed using the Independent Samples t-test. Pre- and post-intervention differences within each group will be assessed by the paired t-test. Statistical significance will be set at $p < 0.05$. In addition, effect sizes will be estimated as r values, calculated from the formula t / \sqrt{n} , in accordance with Cohen's d interpretation.

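### VAS pain is read only before and after an eight-session course; averaging three late readings with baseline adjustment would sharpen the 30-patient comparison at little cost

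*Combined protocol and SAP*

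**What the plan says.** The Methods paragraph of the combined protocol and SAP plans a trial "including 30 patients with rheumatoid arthritis", and states: "Participants will be randomly assigned to two groups: kinesio taping or sham taping". On the schedule: "Interventions will be applied twice a week for four weeks". On assessment: "Measurements will be taken before and after the intervention period". Pain on a visual analogue scale is one of four listed outcomes, and none is named as primary.

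The Statistical analysis paragraph says that "continuous variables will be analyzed using the Independent Samples t-test", and then: "Pre- and post-intervention differences within each group will be assessed by the paired t-test". It plans no reading during the course, no averaging of readings, no baseline-adjusted model and no repeated-measures model. It does not say whether the between-group test uses end scores or changes, and it gives no rule for missing readings. No power, target difference, standard deviation (SD) or dropout rate accompanies the sample size.

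**The concern.** Pain in rheumatoid arthritis can vary from day to day. If the end assessment is a single rating, all of that variation enters the comparison of taping with sham. Patients are due for eight taping sessions, so further ratings could be taken without new visits.

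With about 15 patients per arm, the pain comparison can reliably detect only a large difference, so avoidable noise matters. A patient who misses the end assessment also has no value for a comparison based on that reading alone, even after attending the last sessions.

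**Working it through.** **Inputs from the documents.** 30 patients, two arms, 2 × 4 = 8 sessions, one assessment before and one after the course, independent-samples t-test, 0.05 significance level.

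**Assumptions, because the documents are silent.** 1:1 allocation; two-sided test; one rating per occasion; correlation b = 0.6 to 0.8 between late readings, taken as equal for every pair; baseline-to-late correlation a = 0.5; equal variance at each reading.

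**Starting point.** The plan gives no basis for 30, so there is no figure of its own to reproduce. From the noncentral t distribution, 15 per arm with one end reading gives 80% power for a difference of 1.06 SD and 56% power for 0.8 SD.

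**Step 1: average three late readings, unadjusted t-test.** The readings are those before taping at visits 7 and 8 and at the end assessment. Variance relative to one reading is V = (1 + 2b)/3. Equivalent sample size is 30/V. The detectable difference is 1.06 × √V.

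| b | V | Variance cut | Equivalent N | Detectable difference |
|---|---|---|---|---|
| 0.6 | 2.2/3 = 0.733 | 27% | 41 | 0.91 SD |
| 0.7 | 2.4/3 = 0.800 | 20% | 37.5 | 0.95 SD |
| 0.8 | 2.6/3 = 0.867 | 13% | 35 | 0.99 SD |

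The cut is the same if the t-test is run on change from baseline. At a = 0.5 the change has variance V + 1 − 2 × 0.5 = V.

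**Step 2: baseline adjustment alone.** ANCOVA with one baseline and one end reading has relative variance 1 − a² = 1 − 0.25 = 0.75. That is a 25% cut, worth 30/0.75 = 40 patients, with no new data.

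**Step 3: both together.** Relative variance is V − a² = 0.483, 0.550 and 0.617 at b = 0.6, 0.7 and 0.8. Dividing by 0.75 gives 0.644, 0.733 and 0.822. Late averaging therefore removes a further 36%, 27% or 18% beyond baseline adjustment.

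**Step 4: a second baseline reading on a different day.** The mean of two baseline readings has variance (1 + b)/2, so the adjusted variance is V − a²/[(1 + b)/2]. Against 0.75 the ratios are 0.561, 0.675 and 0.785, a cut of 22-44%. This needs two pre-treatment readings some days apart, which the documents do not schedule.

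**Step 5: what if the effect is still building?** Suppose it grows linearly over the eight applications. The three late readings then carry 6/8, 7/8 and 8/8 of the final effect, with mean 0.875. Efficiency relative to a single end reading is 0.875² divided by the variance ratio:

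- Unadjusted: 0.766/V = 1.04, 0.96 and 0.88 at b = 0.6, 0.7 and 0.8.
- Both sides baseline-adjusted: 0.766/0.644 = 1.19, 0.766/0.733 = 1.04 and 0.766/0.822 = 0.93.

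**Step 6: why not average the whole course?** The eight readings from before visit 2 to the end carry on average (1 + 2 + … + 8)/(8 × 8) = 0.56 of the final effect under linear build-up. For a final effect of 0.8 SD, unadjusted power falls to 26-36% over correlations of 0.5 to 0.8, against 56% for the single end reading.

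**The case against.** A pre/post design is legitimate and coherent, and nothing in the plan contradicts itself on this point. A reader might infer that measuring twice is a mistake. The documents do not support that: the comparison is valid as planned, only less precise than it could be.

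A reader might also infer that noise in the ratings is the only imprecision that can be reduced without enrolling more patients. Step 2 shows otherwise: at a = 0.5, adjusting for the baseline already collected nearly matches the best case of late averaging alone (25% against 27%) and exceeds its middle case (20%).

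It is likewise tempting to credit the 18-36% or 22-44% cuts to the planned analysis. They are measured against a baseline-adjusted analysis that the plan does not include. For the planned t-test, only 13-27% applies.

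Three further objections stand as limits:

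- **Changed target.** The endpoint becomes average pain over roughly the last week. Under linear build-up the unadjusted gain disappears or reverses over most of the assumed correlation range.
- **Unstated schedule.** The documents do not say whether the baseline assessment and first taping, or visit 8 and the end assessment, fall on different days. If the last two coincide and their readings agree perfectly, the variance is (5 + 4b)/9 = 0.822, 0.867 and 0.911, and the unadjusted cut shrinks to 9-18%. A same-day second baseline likewise adds little.
- **Unstated measurement details.** Recall period and ratings per occasion are not given. A rating of average pain over a week would already absorb some daily variation.

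Finally, pain is one of four outcomes with no primary named, so the gain does not extend to the trial as a whole.

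**Conclusion.** The point holds as an inexpensive efficiency improvement. With 15 per arm, averaging three late VAS readings cuts the variance of the planned unadjusted comparison by 13-27%, worth about 35-41 patients. Relative to a one-pre/one-post ANCOVA, the cut is 18-36%, on top of the 25% from baseline adjustment.

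These sizes rest on assumed correlations (0.6 to 0.8 between late readings, 0.5 from baseline to end), readings on separate days and a roughly constant effect over the last week. With equal correlations and a constant effect, some variance reduction is certain for any correlation below 1, but its size is not known from the documents. With an effect still building linearly, relative efficiency without adjustment is 1.04, 0.96 and 0.88 at correlations 0.6, 0.7 and 0.8.

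**What to change.** In Methods:

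- Record VAS pain at the baseline assessment, before tape is applied at every session, and at the end assessment, with the same recall period each time.
- State on which days the baseline and end assessments fall relative to the first and last sessions.
- Define the pain endpoint in advance as the mean of whichever readings are available from before visit 7, before visit 8 and the end assessment.

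In Statistical analysis:

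- Compare arms on that endpoint by ANCOVA with baseline VAS as covariate. Average in the reading before the first taping if it falls on a different day from the baseline assessment.
- Report the end reading alone as a sensitivity analysis, so that end-of-course pain is still visible.

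Readings at visits 2 to 6 are not part of the endpoint, but they show whether the effect has levelled off. Averaging repeat Timed Up-and-Go runs at each assessment is an optional addition. No gain is quantified for it, and the documents do not say how many runs are planned.

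The cost is a brief rating at sessions already scheduled and a few sentences of protocol text, provided the assessment days need no extra visits; the documents give no cost figure. The change should be made before patients start treatment, because readings not taken cannot be recovered.

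### The between-group t-test does not say whether post-treatment or change scores are compared, and no baseline-adjusted analysis (ANCOVA) is planned although every outcome has a baseline value

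*Combined protocol and SAP*

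**What the plan says.** The Methods paragraph randomises 30 patients to kinesio taping or sham taping. It lists four outcomes: pain on the Visual Analog Scale, DAS28, the Tampa Kinesiophobia Scale and the Timed Up-and-Go Test. None is named primary. On timing it says: "Measurements will be taken before and after the intervention period". A baseline value is therefore planned for every outcome.

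The statistical analysis paragraph gives the whole between-group analysis of continuous data in one clause: "continuous variables will be analyzed using the Independent Samples t-test". Differences from before to after treatment appear only in the next sentence, and only within arms: "Pre- and post-intervention differences within each group will be assessed by the paired t-test".

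No ANCOVA, baseline covariate, regression or repeated-measures model appears in the document. The t-test clause is general enough to cover baseline characteristics as well, but nothing says how baseline enters the comparison of outcomes between arms.

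**The concern.** The objective is taping against sham, so the independent t-test is the main analysis. Two analysts following the text could run different tests, one on post-treatment scores and one on change scores. If the choice is made after the data are seen, the result for each outcome can depend on it.

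The second issue is efficiency. Neither t-test makes the best general use of the baseline value. The post-score test ignores it. The change-score test subtracts it in full, which adds noise when the pre-post correlation is modest. Neither adjusts properly for a chance difference between arms in the outcome's own baseline, which is likely with about 15 patients per arm. ANCOVA estimates the weight on baseline from the data and leaves no choice of score.

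**Working it through.** **The plan's own figure.** The sample size of 30 cannot be reproduced, because no effect size, SD or power is given. With 15 per arm and a two-sided 5% test, a post-score t-test has 80% power for a difference of 1.06 SD.

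**Inputs.**

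- From the documents: 30 patients, two arms, significance level 0.05, measurements before and after treatment.
- Assumed: 1:1 allocation (15 per arm), two-sided testing, no dropout, effect d in post-score SD units, pre-post correlation r, and k = baseline SD / post SD.

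**Formulas.** Power comes from the noncentral t distribution, and sqrt(2/15) = 0.365.

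- Post-score t-test: df 28, ncp = d / sqrt(2/15).
- Change-score t-test: df 28, ncp = d / [sqrt(1 + k² − 2rk) × sqrt(2/15)].
- ANCOVA: df 27, ncp = d / [sqrt(1 − r²) × sqrt((2/15)(1 + F/28))], averaged over F ~ F(1,28) for the chance baseline difference. The average of 1 + F/28 is 1 + 1/26 = 1.038.

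**Worked case, d = 0.8, r = 0.5, k = 1.**

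- Post score: ncp = 0.8/0.365 = 2.19, power 56.2%.
- Change score: sqrt(1 + 1 − 1) = 1, so the same ncp and power, 56.2%.
- ANCOVA: sqrt(0.75) = 0.866. At the average inflation, ncp is about 0.8/(0.866 × 0.365 × sqrt(1.038)) = 2.48. Power is 66.8%.

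**Power (%) at d = 0.8.**

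| r | Post t-test | Change t-test, k = 1 | Change t-test, k = 0.7 | ANCOVA |
|---|---|---|---|---|
| 0 | 56.2 | 32.2 | 41.0 | 54.6 |
| 0.2 | 56.2 | 38.7 | 48.5 | 56.3 |
| 0.3 | 56.2 | 43.2 | 53.4 | 58.5 |
| 0.5 | 56.2 | 56.2 | 66.3 | 66.8 |
| 0.7 | 56.2 | 77.9 | 84.2 | 82.7 |

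The column k = 0.7 represents an outcome whose baseline spread is narrowed by eligibility. DAS28, limited to 2.6–5.1 at entry, is the obvious candidate. Before the small-sample cost, the variance excess of the change score over ANCOVA is (1 + k² − 2rk) − (1 − r²) = (k − r)². At r = 0.5 this is 0.25 for k = 1 but only 0.04 for k = 0.7. At r = k = 0.7 it is zero, and ANCOVA then pays only its small-sample cost.

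**Other effect sizes at r = 0.5, k = 1 (post / change / ANCOVA).** d = 0.5: 26/26/32%. d = 1.06: 80/80/89%.

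**Difference detectable with 80% power, k = 1, in SD units (post / change / ANCOVA).** r = 0.3: 1.06/1.25/1.03. r = 0.5: 1.06/1.06/0.94. r = 0.7: 1.06/0.82/0.77.

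**Break-even.** ANCOVA overtakes the post-score test at r of about 0.19–0.20. At r = 0 it loses 56.2 − 54.6 = 1.6 points. With equal SDs, the change-score test becomes marginally better only above r of about 0.92.

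**How often the two t-tests disagree on significance (simulation, one outcome, r = 0.2 to 0.7).**

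| d | k = 1 | k = 0.7 |
|---|---|---|
| 0 | 7–9% | 6–7% |
| 0.3 | 14–21% | 11–16% |
| 0.5 | 22–35% | 17–28% |
| 0.8 | 32–38% | 23–32% |
| 1.06 | 20–29% | 16–18% |

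With no true effect, each t-test alone rejects in about 5% of trials (4.9–5.1%). At least one of the two rejects in 8.6–9.4% (k = 1) or 7.8–8.3% (k = 0.7).

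**The case against.** The strongest reply is that two matters of different weight are joined. The unnamed score is a real gap, but a few words cure it. Preferring ANCOVA to a valid t-test is a question of efficiency, and its gain rests on inputs the documents do not give. Below r of about 0.2 ANCOVA gains nothing over the post-score test, and at r = 0.3 it gains only about 2 points. When the baseline spread is narrowed to 0.7 of the post spread, it ties with the change-score test at r = 0.5 and loses slightly at r = 0.7. The DAS28 entry limits may also lower r itself.

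The disagreement rate also depends on the assumed effect. It is highest near d = 0.8, and the Background calls the benefit over sham uncertain. The null figure of 8–9% describes an analyst who runs both tests and reports the better one, which the plan does not propose.

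Much of this stands as a limit on size. The gain is conditional, the disagreement rate should be read as a range, and the null figure is a worst case and not the plan's type I error. None of it settles which score is tested. Nor does it remove the case for ANCOVA: where it loses in the table, it loses by less than 2 points, and where it gains, the gain can be far larger.

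**Conclusion.** The concern holds. The plan's only between-group rule for continuous outcomes leaves the tested score open and uses no baseline covariate, while baseline values of all four outcomes will be collected. This is an open analysis choice and usually a loss of precision. It is not bias, and each t-test alone keeps its 5% level.

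Under the assumptions of 15 per arm, two-sided 5%, d = 0.8 and equal SDs, ANCOVA gains about 2 points (r = 0.3), 11 points (r = 0.5) and 26 to 27 points (r = 0.7) over the post-score t-test. Over the change-score t-test it gains about 15, 11 and 5 points, and that second gain all but vanishes at r = 0.5 and 0.7 when the SD ratio is 0.7. The specification gap does not depend on these inputs. The plan should be changed before analysis. Confidence in the size of the gain is medium, because r and the SDs are unknown.

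**What to change.** For each of the four outcomes, state that the between-group analysis is an ANCOVA with the post-treatment score as dependent variable, treatment group as factor and that outcome's own baseline score as covariate. Report the adjusted mean difference with its 95% confidence interval and p-value, and check the residuals and the common linear slope. Keep an unadjusted independent t-test on post-treatment scores as a sensitivity analysis, and label the within-group paired t-tests as descriptive.

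If the t-test stays as the main analysis, name the score, post-treatment or change, before outcome data are examined.

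The cost is a few sentences in the SAP and one standard SPSS procedure (UNIANOVA), with no new data. The statistical price is one degree of freedom and a small allowance for chance imbalance, under 2 power points if r is near 0, plus the common-slope assumption. The adjustment covers only each outcome's own baseline, not other prognostic factors.

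### Paired t-tests in each arm share the 0.05 threshold with the between-group test, and the plan does not say that only the between-group comparison supports conclusions about taping

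*Combined protocol and SAP*

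**What the plan says.** The Objective paragraph of the combined protocol and SAP is comparative: "The aim of this study is to investigate the effects of kinesio taping compared to sham taping in patients with rheumatoid arthritis". The Methods paragraph describes two arms ("Participants will be randomly assigned to two groups: kinesio taping or sham taping") and one assessment on each side of treatment ("Measurements will be taken before and after the intervention period"). It lists four outcomes (pain VAS, DAS28, Tampa Kinesiophobia Scale, Timed Up-and-Go) and names none as primary.

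The statistical analysis paragraph gives two kinds of test for these outcomes. Between groups, "while continuous variables will be analyzed using the Independent Samples t-test". Within groups, "Pre- and post-intervention differences within each group will be assessed by the paired t-test". One threshold follows for all tests: "Statistical significance will be set at $p < 0.05". The paragraph closes with a single effect size, called r, computed as t/√n and interpreted on the scale of Cohen's d.

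Three things are left open: which of the two tests supports the conclusion, whether the between-group test uses post-treatment values or changes, and whether the paired tests are only descriptive.

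**The concern.** Pre-to-post change in one arm is the sum of any specific effect of the tape and everything else that moved the outcome over four weeks: disease course, response to being treated and attended to twice a week, and measurement effects. The paired test asks whether that sum is zero. The objective asks whether the sum differs between arms, and only the randomised contrast answers that.

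With two paired tests per outcome on the same footing as the between-group test, a report could present 'significant with taping, not significant with sham' as a benefit of taping, or 'both arms improved significantly' as evidence that both work. The first reading compares two p-values instead of two means. The second attributes to treatment a change that has no comparator. At stake is a claim of benefit on pain, kinesiophobia, mobility or disease activity that the randomised comparison does not support.

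**Working it through.** The plan gives no power calculation, SD or expected change, so it has no figure of its own to reproduce.

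**Inputs from the document**
- Total sample size 30 (Methods).
- Significance level 0.05 (statistical analysis paragraph).
- Paired t-test in each arm and independent t-test between arms (same paragraph).

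**Assumptions**
- 1:1 allocation, so 15 per arm; the ratio is not stated.
- Two-sided tests; sidedness is not stated.
- Approximately normal change scores, with the same SD in both arms.
- No true difference between taping and sham. Both arms share a true improvement of d SDs of the change score, with d varied from 0 to 1.0.

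**Step 1: chance that one arm shows a significant improvement.** The paired t statistic has 14 degrees of freedom, critical value 2.145 and noncentrality d√15. Let p be the probability of exceeding 2.145 in the direction of improvement.

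**Step 2: chance of the misleading pattern.** The arms are independent, so the chance that taping is significant and sham is not is p(1 − p).

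| Shared improvement d | d√15 | p | p(1 − p) |
|---|---|---|---|
| 0 | 0 | 0.025 | 0.025 × 0.975 = 0.024 |
| 0.3 | 1.16 | 0.190 | 0.190 × 0.810 = 0.154 |
| 0.5 | 1.94 | 0.438 | 0.438 × 0.562 = 0.246 |
| 0.7 | 2.71 | 0.713 | 0.713 × 0.287 = 0.205 |
| 0.8 | 3.10 | 0.821 | 0.821 × 0.179 = 0.147 |
| 1.0 | 3.87 | 0.949 | 0.949 × 0.051 = 0.048 |

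The product cannot exceed 0.25. It reaches that value where p = 0.5, near d = 0.55.

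**Step 3: the between-group test under the same conditions.** A shared shift cancels in the difference between arms, so a two-sided test on change rejects in 5% of trials whatever d is, and wrongly favours taping in half of those, 2.5%. Simulation of 100,000 trials per setting gave two-sided rejection rates of 4.9%, 4.9% and 5.1% at d = 0.3, 0.5 and 0.8.

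**Step 4: which test the effect size belongs to.** For a paired test, t = mean change / (SD of change / √n), so t/√n is exactly mean change divided by SD of change. For an independent t-test with equal arms and total N, Cohen's d is 2t/√N. With N = 30 that is 0.365t. The plan's formula gives 0.183t with n = 30 (half of d) or 0.258t with n = 15 (d divided by √2). The formula therefore yields a standardised difference for the paired test but not for the taping-versus-sham test.

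**The case against.** The strongest reply is that the right test is already planned. The between-group t-test is named before the paired one, and with randomisation and a sham control it addresses the objective. Nothing in the plan says that efficacy will be inferred from paired tests or from a pattern of significance across arms, and silence on interpretation in a one-paragraph plan is not an intention to misinterpret. This stands: a reader might infer that the trial has no valid comparison or will rely on within-arm results, and the document supports neither.

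Two other inferences also go too far. One is that the lack of an untreated arm is a design defect. The question is taping versus sham, the sham arm is the control for it, and an untreated arm would not make it valid to compare separate paired tests. The other is that regression to the mean will inflate improvement. DAS28 is both an entry criterion and an outcome, but the entry window of 2.6 to 5.1 has two limits, so the net direction is unknown, and no entry threshold is given for the other three outcomes. The argument does not need it, because any shared change has the same consequence.

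The objection that the chance figures depend on the assumed shift is also right, which is why the range includes both ends. Finally, a 95% CI for an arm's mean change excludes zero exactly when its two-sided p-value is below 0.05. Replacing p-values by per-arm intervals would therefore change little by itself; the rule on interpretation does the work.

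What the reply does not remove is the missing hierarchy. The two kinds of test share one threshold, and the only analysis explicitly defined on pre-to-post change, together with the only effect size, is of the kind that cannot answer the objective.

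**Conclusion.** The concern holds as a gap in how the analyses are ranked and interpreted, not as a missing or invalid primary comparison. If within-arm significance were read as evidence for taping, the chance of a false signal in its favour on one outcome would run from about 2% with no shared improvement, through 15% at 0.3 SD, 25% at 0.5 SD, about 20% at 0.7 SD and 15% at 0.8 SD, to 5% at 1.0 SD, against 2.5% for a between-group test on change. The excess is therefore large for moderate shared improvement and small at either extreme. These figures rest on 15 per arm, normal changes with equal SDs, and assumed shifts for which the document gives no basis; they describe one outcome, not all four. The logical point, that a within-arm change cannot answer a between-arm question, needs none of these assumptions. The point merits correction before analysis but does not invalidate the trial.

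**What to change.** Amend the statistical analysis paragraph as follows.

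- State that conclusions about taping rest only on the between-group comparison for each outcome. Define that comparison as either the difference in pre-to-post change or the post-treatment value adjusted for baseline, and report it with its 95% CI.
- Replace t/√n with a between-group effect size; for an unadjusted equal-arm comparison, Cohen's d is 2t/√N.
- Report mean change in each arm descriptively, without significance tests. State that it will not be interpreted as an effect of taping or of sham, and that the arms will not be compared by which one reached significance.

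This takes a few sentences and needs no extra patients, visits or measurements. The cost is the loss of the within-arm p-values. The change should be made before results are seen, so that the choice of comparison cannot be influenced by them.

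### No primary outcome is named and four outcomes are each tested at p < 0.05: at assumed correlations of 0 to 0.7, the chance of at least one false KT–sham difference in either direction is about 13–19%, against 5% for one test

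*Combined protocol and SAP*

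**What the plan says.** The outcomes appear in one sentence under Methods: "Outcomes will include pain (Visual Analog Scale), disease activity (DAS28), kinesiophobia (Tampa Kinesiophobia Scale), and functional mobility (Timed Up-and-Go Test"). None is called primary. The Objective is no more selective; it states its aim "with a particular focus on pain, functional mobility, kinesiophobia, and disease activity".

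The two titles differ in scope. The official title covers the same four domains as the Objective. The second title is worded "in Terms of Pain, Function and Kinesiophobia" and leaves out disease activity.

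The Statistical analysis paragraph covers all between-group comparisons of continuous outcomes in one clause: "continuous variables will be analyzed using the Independent Samples t-test". One threshold follows: "Statistical significance will be set at" p < 0.05. The paragraph runs from software to effect size without an ordering of outcomes, a multiplicity adjustment or a criterion for a positive trial. It also does not say whether the variable compared between groups is the pre-to-post change or the post-intervention score.

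**The concern.** Four outcomes of equal rank, each tested at 5%, give four chances of a significant result. The plan does not say that one significant outcome is enough to call the taping effective, but nothing in it excludes that reading. The outcome to headline could therefore be chosen once the results are known.

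In a trial of 30 patients, one significant outcome out of four is weaker evidence than its p-value suggests, because that p-value takes no account of the other three attempts. The difference between the titles adds to the uncertainty, since it is unclear whether disease activity belongs to the effectiveness question at all.

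**Working it through.** The plan gives no overall error rate and no derivation of its sample size, so there is no figure of its own to reproduce beyond the 0.05 per test.

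**Inputs from the document**
- Four outcomes (Methods)
- Two groups, 30 patients in total (Methods)
- Measurement before and after the intervention period, so one post-treatment comparison per outcome (Methods)
- t-test for each continuous variable, p < 0.05 (Statistical analysis)

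**Assumptions, not in the document**
- Two-sided tests
- 15 patients per arm
- Normal outcomes with one common correlation
- No true KT–sham difference on any outcome

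The within-group paired t-tests are left out because they do not compare KT with sham.

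**Independent outcomes, exact**
- At least one p < 0.05, either direction: 1 − 0.95^4 = 0.1855
- At least one favouring KT: 1 − 0.975^4 = 0.0963
- Only the three outcomes of the second title, either direction: 1 − 0.95^3 = 0.1426

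**Correlated outcomes.** Simulation with 100,000 trials per setting, pooled two-sided t-tests on 28 degrees of freedom. The simulation error is about √(0.15 × 0.85 / 100,000) = 0.001. The column for correlation 0 is the exact result.

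| Chance of at least one p < 0.05 | 0 | 0.3 | 0.5 | 0.7 | 0.9 | One test |
|---|---|---|---|---|---|---|
| Four outcomes, either direction | 18.5% | 17.5% | 15.8% | 13.2% | 9.4% | 5% |
| Four outcomes, favouring KT | 9.6% | 8.8% | 7.8% | 6.5% | 4.7% | 2.5% |
| Three outcomes, either direction | 14.3% | 13.6% | 12.8% | 10.9% | 8.4% | 5% |

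Repeating the first row with 400,000 trials per correlation gave 18.6%, 17.3%, 15.8%, 13.3% and 9.4%.

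**Unequal arms.** With 12/18 the four-outcome, either-direction figures at correlation 0, 0.5, 0.7 and 0.9 are 18.5%, 15.7%, 13.3% and 9.5%. With 10/20 they are 18.5%, 15.8%, 13.3% and 9.6%. All are within 0.5 percentage points of the equal-arm values.

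**Error rate of the remedy.** Take one primary at 0.05 and the other three tested by Holm.
- Holm run whatever the primary shows, independent outcomes: 1 − 0.95 × (1 − 0.05/3)^3 = 0.0967. At correlation 0.7 the simulated figure is 7.4%.
- Holm run only if the primary is significant: 5%. With no true differences, a false claim then requires the primary test itself to be falsely significant.

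**Price for the secondaries.** The first Holm threshold is 0.05/3 = 0.0167. Noncentral-t power at 15 per arm:

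| Threshold | Difference detectable with 80% power | Power at 0.8 SD |
|---|---|---|
| 0.05 | 1.06 SD | 56% |
| 0.0167 | 1.25 SD | 38% |

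**The case against.** The strongest objection is that 13–19% is the error rate for declaring success if any one outcome is significant, and the plan states no such rule. If the four outcomes are read as four separate questions, each test keeps its 5%. This is right as far as it goes. The documents show an omission, and a false effectiveness claim at that rate depends on how the results are used. But the figure quoted is the chance of at least one false difference when the tests are run as written, and it needs no success rule. Without any rule, the plan also cannot claim 5% for its overall conclusion.

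A second objection is that the range stops at a correlation of 0.7 and counts both directions. At 0.9 the figure is 9.4%, and the chance favouring KT is lower in absolute terms throughout. Both points are fair, which is why the full table is given. No correlation examined brings either figure down to its single-test value.

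Third, the shortened second title is thin evidence of a different outcome set, since the official title, the Objective and the outcome list agree on four. That is accepted; the concern does not depend on it.

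Fourth, making pain decisive narrows an objective that gives all four domains equal weight. Holm or Bonferroni across all four would also control the error rate: at 0.05/4 = 0.0125 each, 1 − (1 − 0.0125)^4 = 4.9% for independent outcomes. That is a legitimate alternative if the sponsor wants equal standing, but no outcome would then be assured the full 0.05. The choice is the sponsor's, but it has to be made in advance.

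**Conclusion.** The concern holds. Run as written, the four unadjusted between-group tests give about a 13–19% chance of at least one false KT–sham difference at correlations of 0.7 down to 0, and 9.4% at 0.9, against 5% for one test. In the direction favouring KT it is 6.5–9.6% over correlations of 0.7 to 0, and 4.7% at 0.9, against 2.5%.

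The figures rest on two-sided testing, normal outcomes with a common correlation, and equal arms, although unequal arms barely matter. The size depends on the correlation, which the documents do not give. The missing primary outcome and missing decision rule do not depend on any of these assumptions. This must be fixed, because the plan does not say what its conclusion rests on and naming a primary loses most of its value once results are known.

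**What to change.** Before the data are seen:

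1. Name one primary between-group comparison. VAS pain at the end of the four weeks is the natural candidate, because pain comes first in both titles, the Objective and the outcome list. The sponsor should confirm it.
2. State whether the variable is the pre-to-post change or the post-intervention score.
3. Test it two-sided at 0.05 and base the effectiveness conclusion on it alone.
4. Report the other three outcomes as secondary, in one of two ways: (a) estimates with 95% confidence intervals and no significance claims; or (b) Holm-adjusted tests, carried out only if the primary is significant. The condition in (b) is necessary once the primary has used the full 0.05.

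If outcome data have already been seen, the choice of primary should be labelled post hoc and all four outcomes reported.

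**Cost.** Wording only, in the Statistical analysis paragraph and, for consistency, in the Objective and Methods. Patients, visits and measurements do not change. The primary keeps its full 0.05, but at 15 per arm the conclusion then rests on a single test with 56% power for a 0.8 SD difference.

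The secondaries bear the loss. Under (a) they carry no significance claims. Under (b) they face a first threshold of 0.0167 and are not tested if the primary fails. If all four outcomes truly differ by 0.8 SD, power for each secondary after both the condition and Holm is about 24%, 34% and 37% at correlations of 0, 0.5 and 0.7, against 56% for an unadjusted test.
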